10.2 Analysis Populations

The analysis populations for Module 1 Part A and Part B are summarised in [Table 6](#).

Table 6 Module 1 Part A and Part B Analysis Populations

| Analysis population /Analysis set | Description | Endpoint/Output |
|-----------------------------------|--|---|
| Enrolled/Screened | All patients who sign the ICF | Disposition |
| Safety | All patients who received at least 1 dose of AZD0466. For safety analyses, participants will be reported by the actual treatment(s) received and grouped by their assigned target dose level of AZD0466 | Demography Baseline Exposure Safety Performance status PK concentrations and parameters listings |
| Intent-to-treat | All patients who received at least 1 dose of AZD0466 | OS PFS ORR |
| Evaluable for Response | All patients, with measurable disease at baseline, who have | ORR DoR |

| | | |
|------------------|---|---|
| | received at least 2 doses of AZD0466 at the target dose level in Cycle 1 | CR rate TTR |
| DLT Evaluable | Patients enrolled in dose escalation who have received at least 2 doses of AZD0466 at the target dose level (67% of target doses from Day 8 to Day 22 in Cycle 1) and have completed the safety follow-up through the DLT evaluation period or have experienced a DLT | DLT |
| Pharmacokinetics | Dosed patients with reportable plasma concentrations and no important AEs or protocol deviations that may impact PK | Plasma concentrations and derived PK parameters |

DLT = dose-limiting toxicity; PK = pharmacokinetics; ICF = informed consent form; PFS = progression free survival; TTR=Time to response, OS = overall survival; DoR = duration of response; ORR = overall response rate; CR = complete response.

10.3 General Considerations

Refer to Section [4.3](#) of this SAP.

10.3.1 Visit Window

Refer to Section [4.3.4](#) of this SAP.

An example of visit windows for physical examination data up to Cycle 3 Day 1 for Module 1 are given below:

- Cycle 1 Day 8 (Study Day 8): 2-11
- Cycle 1 Day 15 (Study Day 15): 12-18
- Cycle 1 Day 22 (Study Day 22): 19-25
- Cycle 2 Day 1 (Study Day 29): 26-32
- Cycle 2 Day 8 (Study Day 36): 33-39
- Cycle 2 Day 15 (Study Day 43): 40-46
- Cycle 2 Day 22 (Study Day 50): 47-53
- Cycle 3 Day 1 (Study Day 57): 54-60

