4.3.4 Visit Window

Visit windows will be defined for any presentations that summarize values by visit. The following conventions will apply:

- Visit windows will be exhaustive so that data recorded at any timepoint has the potential to be summarized. Inclusion within the visit window will be based on the actual date and not the intended date of the visit.
- The window for the visits following baseline will be constructed in such a way that the upper limit of the interval falls halfway between the 2 visits (the lower limit of the first post-baseline visit will be Day 2). If an even number of days exists between 2 consecutive visits, then the upper limit will be taken as the midpoint value minus 1 day.
 - Examples applicable to each module will be defined separately for that module.
- Visit windowing will be conducted up to and including the end of treatment visit. That is, the end of treatment visit will be reassigned a scheduled visit based on the study day the end of treatment visit occurred at.
- If there are more than one value per patient within a time window then the closest value to the scheduled visit date are summarised, or the earlier, in the event the values are equidistant from the nominal visit date. The listings highlight the value for the patient that contributed to the summary table, wherever feasible. Note: in summaries of extreme values, all post baseline values collected are used including those collected at unscheduled visits regardless of whether or not the value is closest to the scheduled visit date.
- For summaries at a patient level, all values are included, regardless of whether they appear in a corresponding visit based summary, when deriving a patient level statistic such as a maximum.
- Visit windowing will be done separately for each assessment based on the schedule of events specific to that assessment.
- Should Study Day be missing (due to partial or missing dates), then visit will be assigned to the nominal visit at which that assessment was recorded, and no windowing will be performed.
- For summaries showing the maximum or minimum values, the maximum/minimum values recorded while on study treatment will be used (regardless of where it falls in an interval).

- Listings should display all values contributing to a timepoint for a patient.

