5.6 Safety Analyses

The domain safety covers exposure, adverse events, clinical laboratory, vital signs, ECG, B-symptoms, and tumour lysis syndrome (TLS).

Tables will be provided for the SAF, listings are provided for all patients or the SAF depending on the availability of data.

All safety analysis will be presented by dose level/cohort. The results from the ramp-up period will be presented separately.

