14 APPENDIX

The schedule of activities for Module 1 Part A and Part B is presented in [Table 7](#) for screening and Cycle 1 and in [Table 8](#) for Cycle 2 and beyond and follow-up.

Table 7 Schedule of Activities for Module 1 Part A and Part B: Screening and Cycle 1

| Procedure | Screening | Cycle 1 (28 days) | | | | | | | | | | Details in CSP section or appendix |
|----------------------------------|-----------|---|---|---|---|-------------|---|----|----|----|----|------------------------------------|
| | | Ramp-up | | | | Target dose | | | | | | |
| Day | -28 to -1 | 1 | 2 | 4 | 5 | 8 | 9 | 10 | 11 | 15 | 22 | |
| Visit window | | ± 2 days (unless indicated otherwise) | | | | | | | | | | |
| Informed consent | X | | | | | | | | | | | A 3 |
| Inclusion and exclusion criteria | X | | | | | | | | | | | 5.1, 5.2, 10.5.1, , 10.5.2 |
| Demography | X | | | | | | | | | | | 8 |
| Medical history | X | | | | | | | | | | | 8 |
| Disease characteristics | X | | | | | | | | | | | NA |
| Disease prognostic scores | X | | | | | | | | | | | Appendix M |
| Physical examination | X | X | X | X | X | X | | | | X | X | 8.2.1 |
| Height | X | | | | | | | | | | | 8.2.1 |
| Weight | X | X | | | | X | | | | | X | 8.2.1 |
| Vital signs | X | X | X | X | X | X | X | | | X | X | 8.2.2 |
| ECOG performance status | X | X | | | | | | | | | | 8.2.5.2 |
| Concomitant medication | X | X | X | X | X | X | | | | X | X | 6.5 |
| Adverse events | X | X | X | X | X | X | X | | | X | X | 8.3 |
| Safety ECGs (triplicate) | X | X | X | X | X | X | X | | | X | X | 8.2.3, 10.8.2.3 |

| | | | | | | | | | | | | | |
|--|---|--|--|---|--|----------------|--|--|--|---|---|--|--------------------|
| 24-hour continuous 12-lead ECG (Holter) recording for PK purpose | | | | | | X ^a | | | | | | | 8.2.3, 10.8.2.3 |
| Cardiac MUGA/MRI/ECHO | X | | | | | | | | | | | | 8.2.5.1 |
| Fresh or archival tumour sample | X | As clinically indicated | | | | | | | | | | | 10.8.6.3 |
| Laboratory tests | | | | | | | | | | | | | |
| SARS-CoV-2 test | X | | | | | | | | | | | | 8.2.4 |
| Pregnancy test (WOCBP) | X | X | | | | | | | | | | | 8.2.4 |
| Haematology | X | X | | X | | X | | | | X | X | | 8.2.4 |
| Clinical chemistry | X | X | | X | | X | | | | X | X | | 8.2.4 |
| Serum immunoglobulins | X | | | | | X | | | | | | | 8.2.4 |
| Beta-2 microglobulin | X | | | | | X | | | | | | | 8.2.4 |
| Amylase and lipase | X | X | | X | | X | | | | X | X | | 8.2.4 |

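### The SAP's visit-window example breaks its own rule, Day 1 post-dose values have no window, and the tie rule removes end-of-infusion ECGs from by-visit summaries

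*SAP*

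**What the plan says.** SAP 4.3.4 sets the general rules. Windows are built separately for each assessment from its own schedule and are assigned by actual date. They are meant to leave nothing out: "Visit windows will be exhaustive so that data recorded at any timepoint has the potential to be summarized". For the start, "the lower limit of the first post-baseline visit will be Day 2"; for each boundary, "the upper limit of the interval falls halfway between the 2 visits", less one day when an even number of days separates the visits. If a window holds several values, the SAP uses the "closest value to the scheduled visit date are summarised, or the earlier, in the event the values are equidistant from the nominal visit date".

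SAP 10.3.1 gives the only worked case: "An example of visit windows for physical examination data up to Cycle 3 Day 1 for Module 1 are given below". Its first line is "Cycle 1 Day 8 (Study Day 8): 2-11". The schedule in SAP Table 7 marks screening and Days 1, 2, 4, 5 and 8 for this assessment: "Physical examination | X | X | X | X | X | X". Protocol Table 13 agrees.

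SAP 5.6 adds: "The results from the ramp-up period will be presented separately". SAP 5.6.9.2 summarises ECG parameters and their changes from baseline by visit, and plans box plots for each time point.

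**The concern.** Three things do not fit together. The example treats Day 8 as the first post-baseline visit for an assessment that is scheduled three times between Day 1 and Day 8. A first window that opens on Day 2 leaves nowhere for values taken after the first infusion on Day 1. And a tie rule that works in days cannot tell a pre-infusion reading from an end-of-infusion reading on the same date.

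The second and third matter more. Change from baseline in ECGs and vital signs is part of the Part A primary endpoint (SAP Table 1), and protocol Table 1 lists cardiovascular toxicity, including QRS changes, as an important potential risk. If the rules are programmed as written, the by-visit ECG tables show pre-infusion values on every dosing day and never the value at the end of an infusion.

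**Working it through.** **Inputs.** Scheduled days after first dose in Cycle 1 (SAP Table 7, protocol Table 13): physical examination on Days 2, 4, 5, 8, 15 and 22; ECG and vital signs on the same days plus Day 9; haematology on Days 4, 8, 15 and 22. ECG time points come from protocol Table 16. Blood pressure is taken at each PK time point (protocol 8.2.2 with Table 17).

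**Step 1: reproduce the printed windows.** The midpoint of visits a and b is (a + b)/2. For Days 8 and 15 it is 11.5, giving an upper limit of 11. For Days 15 and 22 it is 18.5, giving 18, and so on. The seven windows from Day 15 to Day 57 all reproduce, as does the upper limit of 11 for Day 8. The lower limit of 2 for Day 8 appears only if Days 2, 4 and 5 are deleted from the schedule.

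The even-gap rule can be read in two ways: (A) count the days strictly between the visits, or (B) take the difference between the visit days. Both reproduce the weekly windows.

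**Step 2: apply the rule to the scheduled physical-examination days.**

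| Visit | Midpoint to next visit | Window (A) | Window (B) |
|---|---|---|---|
| Day 2 | (2 + 4)/2 = 3 | 2-3 | 2 |
| Day 4 | (4 + 5)/2 = 4.5 | 4 | 3-4 |
| Day 5 | (5 + 8)/2 = 6.5 | 5-6 | 5-6 |
| Day 8 | (8 + 15)/2 = 11.5 | 7-11 | 7-11 |

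Day 8 is 7-11 on either reading, not 2-11.

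For ECG and vital signs, Days 2, 4 and 5 get the same windows as above. Day 8 becomes 7-8, from (8 + 9)/2 = 8.5. Day 9 becomes 9-12 (A) or 9-11 (B), from (9 + 15)/2 = 12. For haematology, Day 4 is 2-6 and Day 8 is 7-11 (A), or 2-5 and 6-11 (B).

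**Step 3: Study Day 1.** SAP 4.3.3 makes the date of first dose Study Day 1 and treats anything collected after first dose as post-baseline. The end-of-infusion ECG on Day 1 is therefore post-baseline, but no window contains Day 1.

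**Step 4: same-day ties, using the correct per-assessment ECG windows.** Table 16 has 12 Cycle 1 safety ECG time points after the first dose:

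- Single time points: Day 1 end of infusion, Day 2, Day 5, Day 9 (4).
- Pre-infusion and end-of-infusion pairs: Days 4, 8, 15, 22 (4 × 2 = 8).

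A pair shares one date, so both members are equally far from the nominal visit, and the earlier, pre-infusion one is used. Kept: Days 2, 5 and 9 and the pre-infusion ECGs of Days 4, 8, 15 and 22, which makes 7. Lost: 12 − 7 = 5, namely the end-of-infusion ECGs of Days 1, 4, 8, 15 and 22. Day 1 is lost for want of a window and the other four through the tie rule. Adding the pairs on Cycle 2 Days 1 and 8 gives 5 + 2 = 7 lost.

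Blood pressure on Day 8 has 6 same-day time points (pre-infusion, 30 minutes, end of infusion, 2, 6 and 9 hours). One is kept and 6 − 1 = 5 are displaced.

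**Step 5: look for a rule that rescues these values.** The same-day rule in 4.3.4 covers only a repeat made because something was wrong with the first measurement. SAP 5.6.9.1 averages triplicates only. Neither separates planned time points.

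**The case against.** The strongest reply is that the 2-11 window is an example for one assessment and feeds no specified table. SAP 5.6 describes no by-visit physical-examination output, and physical examination is a Part B secondary endpoint. That stands. A reader might infer that all ramp-up visits are folded into Day 8. The documents do not support this: under 4.3.4, ECG and vital signs have their own Day 2, 4 and 5 windows, and haematology has a Day 4 window. Only if the example were copied to ECGs, against 4.3.4, would just 3 of the 12 Cycle 1 ECG time points survive (pre-infusion Days 8, 15 and 22).

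A reader might also infer that values after the 300 mg ramp-up dose would generally be labelled as the 600 mg visit at dose level 1. That does not follow for ECG or vital signs, because a Day 5 value falls in the Day 5 window. A pre-infusion Day 8 value precedes the first target dose however the windows are drawn.

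Nor do the documents show that the separate ramp-up results or the time-point box plots cannot be produced. Windows govern by-visit summaries only, and the table specifications are in a separate document. The SAP does not forbid working by time point. It simply does not say how time point and windowing relate.

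Finally, much is untouched. Extreme-value summaries use all post-baseline values, so the notable QTcF counts stand, and listings keep everything. The schedule shows no paired laboratory draws, and by-visit vital-sign tables are optional (SAP 5.6.6.2). One could also say the tie rule was meant for values on different dates. That may be so, but nothing in the text limits it that way.

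**Conclusion.** The point holds in a limited form.

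1. The physical-examination example contradicts SAP 4.3.4 and the schedule; Day 8 should be 7-11. The error is confined to that example.
2. Study Day 1 post-dose values have no window, contrary to the stated aim of exhaustive windows.
3. Read literally, the tie rule keeps the pre-infusion value over same-day later ECGs and blood pressures. All 5 Cycle 1 end-of-infusion ECGs, or 7 up to Cycle 2 Day 8, are absent from the by-visit descriptive summaries even with correct windows.

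The counts assume visits on their nominal days and a pre-infusion ECG present in each pair. The tie itself does not depend on nominal timing, since both members of a pair share a date. No redacted figure is needed. What is at risk is the descriptive by-visit picture of change after infusion. Detection of extreme values is not affected.

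**What to change.** In the SAP:

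- Reprint the 10.3.1 example from the scheduled days, with Day 5 as 5-6 and Day 8 as 7-11. State which even-gap reading applies, since it decides whether Days 2 and 4 are 2-3 and 4, or 2 and 3-4.
- Add a Day 1 post-dose category.
- State that windowing and the closest-else-earlier rule apply within planned time point (pre-infusion, end of infusion, later hours), so that they choose only between repeats of the same time point. State that the box plots use the same time points.
- State how the ramp-up windows feed the separate ramp-up presentation in 5.6.

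The cost is SAP wording, some reprogramming and slightly longer by-visit tables. Data collection does not change.

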10.3.2 Handling of Unscheduled Visits

Refer to Section [4.3.4](#).

10.3.3 Multiplicity/Multiple Comparisons

Not Applicable.

10.3.4 Handling of Protocol Deviations in Study Analysis

Refer to Section 4.3.7.

10.3.5 Sample Size

10.3.5.1 Modified toxicity probability interval-2 (mTPI-2)

The mTPI-2 employs a simple beta-binomial Bayesian model. The posterior density of the toxicity probability is divided into multiple intervals with equal length. These intervals are categorized as underdosing (below), proper dosing (equivalent), and overdosing (above) in terms of target toxicity. The underdosing interval corresponds to a dose escalation, overdosing corresponds to a dose de-escalation, and proper dosing corresponds to staying at the current dose.

For specific dose escalation rules, refer to Section 10.6.6.1 of CSP and Section 10.3.5.2 of SAP.

10.3.5.2 Dose Escalation

Module 1 Part A (Dose Escalation): The primary objective of Part A is to identify the maximum tolerated dose (MTD) of AZD0466 monotherapy. In Module 1 Part A, a minimum of **CC1** patients will be enrolled in a dose cohort and evaluated through the DLT evaluation period of 28 days before a dose escalation/expansion/ de-escalation decision can be made (unless unacceptable toxicity is encountered prior to enrolment of **CC1** patients), while the maximum number of patients to be enrolled in any given dose cohort will be capped at **CC1** patients. Dose escalation (or de-escalation) will be determined by mTPI-2 with a target DLT rate of **CC1**% and an equivalence interval of (**CC1**%, **CC1**%). A dose level will be considered non-tolerated with no additional patients enrolled at that dose level, if it has an estimated 95% or more probability (P) of exceeding the target DLT rate of **CC1** **CC1** with at least **CC1** patients treated at that dose level. Five doses (DL-1, DL1 to DL4, start at DL1), **CC1** total patients, with a maximum of **CC1** being DLT evaluable at each dose level. The structure of the dose escalation part is shown in Figure 1.

[figure not shown]
10.3.5.3 Dose Expansion

Module 1 Part B (Dose Expansion)

Separate expansion cohorts will enrol 3 distinct populations of patients with B-cell non-Hodgkin's lymphoma: patients diagnosed with R/R MCL will be enrolled in Cohort B1, R/R FL or R/R MZL patients in Cohort B2, and R/R DLBCL patients in Cohort B3. Cohorts B1 and B2 will recruit up to **CC1** patients, and Cohort B3 will recruit approximately **CC1** patients. These sample sizes have been determined to ensure confidence intervals constructed around the complete ORR, as calculated after all patients have had the opportunity to complete 2 treatment cycles, will provide sufficient information to enable

decisions to be made around the likely success of future studies in these patient populations, using methodology described in Frewer et al 2016 ([Frewer et al 2016](#)).

CCI

Refer to Section 10.9.2 of the CSP for details of the target values for cohorts B1, B2 and B3.

11 STATISTICAL ANALYSIS – MODULE 1

This section provides information on definitions, derivation and analysis/data presentation per domain.

11.1 Study Population

11.1.1 Patient Disposition and Completion Status

Refer to Section [5.1.1](#) of this SAP.

11.1.2 Analysis Sets

11.1.2.1 Definitions and Derivations

Refer to [Table 6](#) of Section [10.2](#) of this SAP.

11.1.3 Protocol Deviations

Refer to Section [5.1.3](#) of this SAP.

11.1.4 Demographics

Refer to Section [5.1.4](#) of this SAP.

11.1.5 Baseline Characteristics

Refer to Section [5.1.5](#) of this SAP.

11.1.6 Disease Characteristics

Refer to Section [5.1.6](#) of this SAP.

11.1.7 Medical History and Concomitant Disease

Refer to Section [5.1.7](#) of this SAP.

11.1.8 Prior and Concomitant Medications

Refer to Section [5.1.8](#) of this SAP.

11.1.9 Dose-Limiting Toxicity(DLT)

11.1.9.1 Definitions and Derivations

A DLT will be defined as the occurrence of any of the following during the 28-day DLT evaluation period in Cycle 1, unless unequivocally due to underlying malignancy or an extraneous cause. For more details including maximum tolerated dose, refer to Section 10.6.6 of the CSP.

Any event that meets the DLT criteria in the opinion of the Investigator should be reported to the study physician within 24 hours of knowledge of the event. Events will be assessed for DLT criteria according to the NCI CTCAE v5.0 except for TLS, which will be assessed for DLT criteria using the Howard et al 2011 modification of Cairo-Bishop 2004 criteria ([Cairo and Bishop 2004](#)).

Any patient who is not evaluable for DLT assessment will be replaced, with the exception of a patient who experiences a DLT; these patients will not be replaced. Additional patients enrolled at a previously cleared dose level to provide supplemental safety, efficacy, PK, and pharmacodynamics data will not be replaced or evaluated for DLT in support of dose escalation decisions. However, these additional patients will be included in the determination of the MTD/RP2D upon completion of the dose escalation part.

A DLT evaluable patient is defined as a patient enrolled in Module 1 Part A (dose escalation), who has received at least 2 doses of AZD0466 at the target dose level (67% of Cycle 1 after ramp-up) and has completed safety follow-up through the DLT evaluation period, or has experienced a DLT.

During Part A of Module 1, AZD0466 monotherapy dose escalation, AstraZeneca pharmacovigilance process and the SRC will evaluate toxicities study-wide (including evaluation of previous doses). During Part B of Module 1, AZD0466 monotherapy dose expansion, a safety analysis will be performed at the time of the first interim analysis in each cohort (Cohort B1 at CC1 patients, Cohort B2 at CC1 patients) and Cohort B3 at CC1 patients, pooling safety data from all available patients. The study recruitment may be paused, pending investigation by the Sponsor and in discussion with SRC, if CC1 % of patients experience safety events that meet the DLT criteria, see Section 10.6.6.3 of CSP (including AEs of special interest [Section 8.3.6]), the SRC, will decide to stop the study, modify the study, or continue the study, based on the overall risk benefit of the agent. Throughout the expansions, the AZ safety team and the SRC, will regularly review cumulative safety data including, but not limited to, toxicities that meet the DLT criteria.

11.1.9.2 Presentation

The number of Part A dose-setting patients evaluable for determination of DLTs during Cycle 1 and the number of patients with any DLT (and their categorization) will be summarised by dose level and based on the DLT evaluable analysis set. The MTD will be

selected from all tried dose levels that have not been previously declared to be unsafe with a DU decision according to the mTPI-2 algorithm (see CSP Table 15). With this constraint, the MTD will be determined as the dose level with the DLT estimate closest to the target toxicity level of **[REDACTED]**%. The MTD will be determined by isotonic regression analysis applied to Cycle 1 DLT rates observed during dose exploration using the mTPI-2 method (Ji et al 2010).

In the case of dose levels with estimated toxicity of equal distance (tied dose levels) from the target toxicity of **[REDACTED]**%, the following approach is used: among all tied dose levels the highest dose level with target toxicity **[REDACTED]**% will be selected, unless all tied dose levels have estimated toxicity **[REDACTED]**%, in which case the lowest dose level will be selected. Part B patients in Cycle 1 meeting the same criteria for DLT evaluability that were used for Part A dose setting, and the number/percentage of those patients with any safety events that meet the DLT criteria (and their categorization) , will be summarised for Part B RP2D-treated patients.

The number and percentage will be reported for pooled RP2D-treated Part A and Part B patients that experienced at least one safety event that meet the DLT criteria after receiving any amount of study treatment from Cycle 2 onwards. The numbers and types of toxicities that meet the DLT criteria and the cycles (weeks) in which they were observed will also be summarised.

